8.1. Efficacy Assessment and Time Points

8.1.1. [REDACTED]

[REDACTED]

8.1.2. [REDACTED]

[REDACTED]

8.1.3. Tourette Syndrome-Patient Global Impression of Impact (TS-PGII)

The TS-PGIS is administered on baseline (i.e., week 13 data from Study TV50717-CNS-30046 or week 9 data from Study TV50717 CNS-30060) and weeks 4, 8, 15, 28, 34, 41, 54, and 55. Input from the caregiver/adult is permitted.

The TS-PGII is a single-item questionnaire that asks the patient to assess the degree of impact due to current tics. The TS-PGII uses a 5-point scale, ranging from not at all (1) to very much (5), to assess overall response to therapy. In general, patient-rated global measures of change have face validity and have been shown to correlate with disability for a number of chronic conditions.

8.1.4. [REDACTED]

[REDACTED]

This document is confidential.

Statistical Analysis Plan for Interventional Studies

Sponsor: Teva Branded Pharmaceutical Products R&D, Inc./Nuvelution TS Pharma, INC.
Protocol No.: TV50717-CNS-30047

The Tic-free Interval is a 3-item, self-report questionnaire assessing the average number of minutes between tics in patients with TS. Patients rate their symptoms on a 1-to-5 scale, ranging from 1 or more days tic-free (1) to less-than-5-minutes tic-free (5), on their best, worst, and typical days.

8.1.5. [REDACTED]

[REDACTED]

[REDACTED]

- | [REDACTED]
- | [REDACTED]
- | [REDACTED]
- | [REDACTED]
- | [REDACTED]
- | [REDACTED]

[REDACTED]

8.1.6. [REDACTED]

- | [REDACTED]

[REDACTED]

This document is confidential.

8.2. Efficacy Endpoint and Analysis

The following efficacy endpoint will be assessed in Part II and included as key secondary endpoint:

- The change in the TTS of the YGTSS from randomized withdrawal baseline (Week 28) to week 30, with the primary analyses and sensitivity testing done as described in Section 8.2.1.

The following efficacy endpoint will be assessed in Part II and included as exploratory secondary endpoint:

█ [REDACTED]

█ [REDACTED]

The following exploratory efficacy endpoints will be assessed in Parts I and III at the visits in which the data is collected:

█ [REDACTED]

█ [REDACTED]

█ [REDACTED]

█ [REDACTED]

█ [REDACTED]

█ [REDACTED]

█ [REDACTED]

█ [REDACTED]

█ [REDACTED]

█ [REDACTED]

█ [REDACTED]

█ [REDACTED]

█ [REDACTED]

█ [REDACTED]

█ [REDACTED]

█ [REDACTED]

█ [REDACTED]

8.2.1. The change in the TTS of the YGTSS from randomized withdrawal baseline to Week 30

The change will be derived as the assessment value at Week 30 minus the value at the randomized withdrawal baseline (Week 28).

This document is confidential.

Statistical Analysis Plan for Interventional Studies

Sponsor: Teva Branded Pharmaceutical Products R&D, Inc./Nuvelution TS Pharma, INC.
Protocol No.: TV50717-CNS-30047

The observed values at the randomized withdrawal baseline (Week 28) and Week 30, and the change in the TTS of the YGTSS from the randomized withdrawal baseline to Week 30 will be summarized by randomized treatment.

An analysis of covariance (ANCOVA) model will be used as the primary analysis model with the change from Week 28 to Week 30 in YGTSS TTS as the dependent variable, treatment group and age group as fixed effect, and the randomized withdrawal baseline as covariate. The primary analysis will be based on the RRWmITT population. SAS PROC MIXED will be used to carry out this analysis. The SAS code for this test is as follows:

```
proc mixed;  
  class arm avisitn agegrp;  
  model chg=arm base agegrp;  
  lsmeans arm / diff cl stderr;  
run;
```

The least square (LS) mean and standard error for the treatment groups, and the LS mean difference, 95% confidence interval (CI), and p-value for the comparison (TEV-50717 vs. placebo) will be presented at week 30. The LS mean of the change in TTS from week 28 to week 30 will be compared using a 2-sided test at the alpha=0.05 level of significance.

For sensitivity analysis, the same analysis will be repeated for the RWmITT population and a subpopulation of the RRWmITT who had a $\geq 35\%$ reduction in the TTS from the parent study baseline to Week 28.

All summary and analyses will be repeated for each of the age group at entry into the parent study: 6- 11 years and 12- 16 years.

8.2.2. The percent change in the TTS of the YGTSS from randomized withdrawal baseline to Week 30

The same analysis as in Section 8.2.1 will be performed with the percent change used as outcome. No formal hypothesis testing will be done. Nominal p-value will be presented for this exploratory purpose.

8.2.3. Increase in TTS of the YGTSS by $\geq 20\%$ from randomized withdrawal baseline to week 30

Frequency and percentage of patients with increase $\geq 20\%$ from randomized withdrawal baseline to week 30 will be summarized. The binary outcome will be analyzed using logistic regression. SAS PROC LOGISTIC will be used to carry out this analysis. The SAS code for this test is as follows:

```
proc logistic;  
  class arm avisitn agegrp/param=glm;  
  model chg=arm base agegrp;  
  lsmeans arm / diff cl stderr;  
run;
```

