3.5. Determination of Sample Size

This study has 3 key objectives: to assess the long term safety and tolerability of TEV-50717, to evaluate the efficacy of long-term therapy with TEV-50717 in reducing the severity of Tourette syndrome (TS) tics, and to confirm the long-term maintenance of effect by means of a double-blind, placebo-controlled, randomized, 2-week drug withdrawal period after 28 weeks of open-label treatment. The expected number of patients who are anticipated to enroll in this study are based on the patient's dispositions from the parent study ([Table 2](#)).

Table 2: Planned and Actual Sample Size from Parent Study

Study	TV-50717-CNS-30046	TV-50717-CNS-30060	Total
Planned (Actual*) Number of Patients Randomized	116 (109)	150 (117)	
Planned Drop-out Rate in Parent Study (Actual* number withdrawal)	8% (12)	8% (10)	
Planned (Actual*) Number of Patients Completed	107 (91)	138 (85)	
Planned rate of patients that complete parent study	8%	8%	

This document is confidential.

Statistical Analysis Plan for Interventional Studies

Sponsor: Teva Branded Pharmaceutical Products R&D, Inc./Nuvelution TS Pharma, INC.

Protocol No.: TV50717-CNS-30047

and do not enroll in this study			
Planned (Actual*) Number of Patients enroll into this study	99 (79)	127 (78)	226 (157)

** All actual numbers as of the date of 09Aug2019. As the parent studies are ongoing the actual number of subjects enrolled in TV-50717-30047 may differ from the numbers shown in this table.*

For the randomized drug withdrawal period, the potential power by sample size is presented in [Figure 1](#). The study power is computed under the specification below:

- The difference between TEV-50717-treated and placebo-treated patients assuming a difference in the Yale Global Tic Severity Scale (YGTSS) Total Tic Score (TTS) of 4.5;
- Equal standard deviation of 9.0;
- Type 1 error rate of 5%;
- Randomization ratio 2:1 TEV-50717 vs placebo

[figure not shown]
This document is confidential.

Statistical Analysis Plan for Interventional Studies

Sponsor: Teva Branded Pharmaceutical Products R&D, Inc./Nuvelution TS Pharma, INC.

Protocol No.: TV50717-CNS-30047

Figure 1: Power vs. Sample Size

Additional factors that can impact the final sample size for the analyses will include:

1. Patients retention rate before Week 28;
2. Proportion of patients who achieve $\geq 25\%$ reduction in the TTS from baseline in the parent studies to week 28.

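### SAP 8.2.3 describes a binary outcome, but its PROC LOGISTIC code reuses the ANCOVA change score as response and fixes neither the event level nor the direction of the treatment contrast

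*SAP*

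**What the plan says.** Section 8.2.3 concerns patients whose TTS rises by 20% or more between the randomized withdrawal baseline (Week 28) and Week 30. Counts and percentages are to be tabulated. Then: "The binary outcome will be analyzed using logistic regression". The tool is named: "SAS PROC LOGISTIC will be used to carry out this analysis". The code that follows is introduced as the code for this test. Its CLASS statement is "class arm avisitn agegrp/param=glm" and its MODEL statement is "model chg=arm base agegrp". There is no EVENT=, DESCENDING or reference option, and no derived flag. The LSMEANS line asks for arm differences with confidence limits and standard errors, not for odds ratios.

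Section 8.2.1 specifies the key Part II analysis, an ANCOVA "with the change from Week 28 to Week 30 in YGTSS TTS as the dependent variable". That change is defined numerically: "The change will be derived as the assessment value at Week 30 minus the value at the randomized withdrawal baseline (Week 28"). Its PROC MIXED code has the same MODEL and LSMEANS lines as Section 8.2.3.

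Section 8.2.2, between the two, repeats the 8.2.1 analysis with percent change as outcome and prints no code of its own.

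**The concern.** The words and the code of Section 8.2.3 name different responses. This matters because the code is the only place where the model is fixed. The prose gives no covariates, no effect measure, no modelled level and no direction of comparison. A programmer who follows the code analyses something other than the stated endpoint. A programmer who departs from it has to choose the response, the event level and the contrast without a written rule.

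At stake is the meaning of one exploratory Part II result: whether the estimate and p-value belong to the rise of at least 20%, and whether a value below or above 1 favours TEV-50717.

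**Working it through.** The SAP gives no figure for Section 8.2.3, so there is none to reproduce. The check reads the code and illustrates it by simulation.

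**Step 1. What `chg` is.** Section 8.2.1 uses it for the numeric difference, Week 30 minus Week 28. Section 8.2.3 uses the same name in the same MODEL line and defines no 0/1 variable. Both CLASS statements also list `avisitn`, which neither model uses, so the block looks carried over from the ANCOVA.

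**Step 2. Reading A: `chg` is the numeric change.** Given a numeric response with more than two levels, PROC LOGISTIC fits a cumulative logit, by default for lower values:

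logit P(chg ≤ k) = α_k + β·arm + γ·base + δ·agegrp

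The 20% threshold appears nowhere in this model.

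**Step 3. Reading B: `chg` stands for a 0/1 flag.** The endpoint is right. With no event level given, the default models the lower level, 0, meaning no rise of at least 20%. Swapping the modelled level changes the sign of the log odds ratio and leaves the two-sided p-value unchanged.

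**Step 4. Direction also depends on `arm`.** Under GLM coding the last sorted level is the reference. If the arms sort as Placebo, then TEV-50717, the printed difference is Placebo minus TEV-50717, which changes the sign again.

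**Step 5. Illustration.**
- From SAP 3.5: difference 4.5 TTS points, SD 9.0, allocation 2:1, TEV-50717 to placebo.
- Assumed: N = 150; Week 28 TTS mean 20, SD 6; mean change 0 on TEV-50717; whole-point scores, with baselines held between 6 and 50 and Week 30 scores between 0 and 50.

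Each simulated trial had about 39 distinct values of change. Odds ratios are TEV-50717 vs placebo:

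| Simulated trial | Rise ≥20% modelled as event | p | Cumulative logit, lower change | p |
|---|---|---|---|---|
| 1 | 0.34 | 0.0027 | 3.41 | 0.00008 |
| 2 | 0.18 | 0.000011 | 4.01 | 0.000019 |
| 3 | 0.34 | 0.0034 | 2.96 | 0.00049 |
| Median of 6 | 0.44 | 0.046 | 2.58 | 0.0054 |

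The two p-values differ, and not always in the same direction (compare trials 1 and 2). A second set of assumptions (80 and 40 patients, Week 28 SD 7, 60 data sets) gave mean log odds ratios of −0.89 and +0.96: exp(−0.89) = 0.41 and exp(0.96) = 2.6.

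**Step 6. Direction under Reading B, trial 1** (1/0.34 = 2.94, p = 0.0027 throughout):

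| Level modelled | TEV-50717 vs placebo | Placebo vs TEV-50717 |
|---|---|---|
| Rise ≥20% | 0.34 | 2.94 |
| No such rise (default) | 2.94 | 0.34 |

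With the default level and Placebo sorted first, the two reversals cancel and 0.34 is printed. Under Reading A the same reordering turns 3.41 into 1/3.41 = 0.29.

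**The case against.** The strongest reply is that this is a slip in a code skeleton and not a wrong choice of analysis. The prose names the endpoint and the method clearly. The code has no input data set and no derivations. Section 8.2.2 swaps the outcome of the 8.2.1 model without new code, so `chg` may be only a placeholder. On that reading the right endpoint is tested with the right p-value. This stands in part: Reading B is possible, so it cannot be said without condition that the stated endpoint goes unanalysed. But the SAP ties the name `chg` to no flag, and the only use it explains is the numeric one.

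A reader might infer that the code reverses the odds ratio, so that benefit would read as harm. The document does not support that. Step 6 shows that direction depends on two settings, and the code fixes neither. The SAP names no odds ratio for this analysis. The percentages reported alongside would also expose an inverted estimate. Section 8.2.1 does state TEV-50717 vs placebo, but for the ANCOVA; carrying it over would still leave the event level open.

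The contrast between 0.41 and 2.6 shows less than it seems to. It is mostly inversion, since 1/0.41 = 2.4, and it rests on Week 28 values that the SAP does not give.

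Program checking under Section 14 might catch the problem, but it would not correct the plan.

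**Conclusion.** Wrong as written; minor severity. Run literally, the code of Section 8.2.3 fits a cumulative-logit model to the change score, which is a different endpoint with a different p-value. Read charitably, it tests the right endpoint with the right p-value but leaves the sign of the reported effect to SAS defaults and the coding of `arm`. That the direction is unfixed is supported; that it is reversed is not.

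The mismatch follows from the text and code alone. The statements about SAS output rest on PROC LOGISTIC's default ascending response order and on ordinary coding of the variables. The odds ratios and p-values are illustrations under the assumptions listed.

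The reach is limited. The endpoint lists in Sections 4.2 and 8.2 are partly blacked out, but the one key Part II endpoint is the TTS change of Section 8.2.1. Section 11 says two exploratory ones were added to Part II, which leaves Sections 8.2.2 and 8.2.3. The key ANCOVA and its 0.05 test are unaffected.

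**What to change.** Before unblinding, replace the response and state the direction in Section 8.2.3:

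- Derive `flag` = 1 if 100 × (Week 30 − Week 28)/Week 28 is at least 20, and 0 otherwise.
- Code `model flag(event='1') = arm base agegrp;`.
- Set placebo as the reference level of `arm`, so that the contrast is TEV-50717 vs placebo.
- Request the odds ratio with its 95% CI: `lsmeans arm / diff oddsratio cl;`.
- Add one sentence saying that an odds ratio below 1 means lower odds of a rise of at least 20% on TEV-50717.
- Drop the unused `avisitn` from the CLASS statement.

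The cost is a few words of code and one sentence. No data collection, sample size or other analysis changes.

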8.2.4. The Analysis of the Change Scores in Parts I and III Combined

These change scores are included as the exploratory endpoints for Parts I and III combined: the change in the TS-CGI score, the TS-PGII score, the C&A-GTS QOL ADL subscale score, the TTS of the YGTSS, the TS-PGIS score, the YGTSS impairment score, the MTSS of the YGTSS, the VTSS of the YGTSS, the GSS of the YGTSS, VAS in the C&A-GTS QOL score, CY-BOCS scores, and the C&A-GTS QOL total

This document is confidential.

Statistical Analysis Plan for Interventional Studies

Sponsor: Teva Branded Pharmaceutical Products R&D, Inc./Nuvelution TS Pharma, INC.
Protocol No.: TV50717-CNS-30047

and subscale score, tic-free score, the percent change in the TTS of the YGTSS from baseline to each visit.

These changes will be derived as the assessment value minus baseline. The observed values and the changes from baseline will be summarized at each visit in which the scale is administered, including Week 28, but not Week 30 visit if assessed. The summary will be based on the ITT Analysis Set.

8.2.5. Proportion of Patients with Improvement on the TTS of the YGTSS and TS-CGI for Parts I and III Combined

Proportion of patients who have $\geq 25\%$ reduction, $\geq 35\%$ reduction from baseline on the TTS of the YGTSS to each visit, $\geq 25\%$ reduction from baseline of the parent study to each visit, a reduction of ≥ 1 point in the TS-CGI score from baseline to each visit will be analyzed. Frequency, and proportion will be presented at each visit for the ITT Analysis Set in the Parts I and III combined. Summary tables will include one column for all patients. All visits, including Week 28, will be included, but not Week 30.

This document is confidential.

9. Safety

For by-visit safety endpoints, e.g. vital sign, CDI-2, summaries will be presented for:

- The observed values and the change from baseline. The change will be derived as the observed value at the specific visit minus the baseline. Week 30 assessments will not be included. Analyses will be based on the Safety Analysis Set with an overall column.
- The observed values and the change from Week 28 to Week 30. The change will be derived as the observed value at Week 30 minus the randomized withdrawal baseline. Tables will be based on the RWSAF population and presented by actual treatment received during randomized drug withdrawal period and overall. This will only be included if assessment is performed at Week 30 visit.

For safety endpoints of adverse event and exposure, summary will be presented for:

- Parts I and III combined;
- Part II;
- Parts I, II, and III combined and for each Parts;
- Periods.

The following safety endpoints will be assessed in Parts I and III combined:

- The incidence of adverse events
- The observed values and changes from baseline in vital signs
- The observed values and changes from baseline in the CDI-2
- The observed values in the C-SSRS
- The observed values in ECG parameters and shifts from parent study baseline for clinically significant abnormal findings
- The observed values and changes from baseline in clinical laboratory parameters (hematology, serum chemistry, and urinalysis)

The following safety endpoint will be assessed in Part II:

- The incidence of adverse events;
- The observed values and changes from randomized withdrawal baseline (Week 28) in vital signs;
- The observed values and changes from randomized withdrawal baseline (Week 28) in the CDI-2;
- The observed values in the C-SSRS.

9.1. Extent of Exposure

Descriptive statistics will be presented for:

- Duration of exposure to study medication in Parts I, II and III combined, based on Safety Analysis Set and Weeks on treatment using the categories ≤ 28 weeks, >28 to ≤ 54 weeks, >54 weeks;
- Duration of exposure to study medication in each Part;
- Duration of exposure to study medication in Parts I and III combined, based on Safety Analysis Set and Weeks on treatment using the categories ≤ 28 weeks, >28 to ≤ 52 weeks, >52 weeks;
- Duration of exposure in Part II based on the RWSAF Population.

This document is confidential.

Statistical Analysis Plan for Interventional Studies

Sponsor: Teva Branded Pharmaceutical Products R&D, Inc./Nuvelution TS Pharma, INC.
 Protocol No.: TV50717-CNS-30047

9.2. Treatment Compliance

Study drug administration and accountability during open-label portion collect information of the assigned total daily dose in mg, date time of the first and the last dose, and the number of pills taken per dose strength (6, 9, and 12 mg). Study drug administration and accountability during blinded portion collect information of study week, date time of the first and the last dose, number of pills taken per bottle. The compliance is computed in sequence below:

The total number of pills taken=sum (the number of pills taken from all bottles dispensed, identified by med ID);

The number of pills expected = sum (the number of pills should be taken per schedule for all bottles dispensed (Table 4 and Table 5), identified by med id or bottle dose strength) ;

Treatment compliance (%) = 100*(total number of doses taken / number of doses expected to be used).

Table 4: Part I Titration, Maintenance Phases and Part III Maintenance Administration Instructions

Daily Dose	First Kit Type Needed		Second Kit Type Needed		Administration Instructions
	# Tablets Per Day	Tablet Strength	# Tablets Per Day	Tablet Strength	
6 mg	1	6 mg	n/a	n/a	Enrollment Day 1 In Clinic: Day 1: 6 mg: Take 0 tablets AM and 1 tablet PM Day 2–7: 6 mg: Take 1 tablet AM and 0 tablets PM All Other Visits: 6 mg: Take 1 tablet AM and 0 tablets PM
6 /12 mg	1	6 mg	n/a	n/a	Day 1: 6 mg: Take 0 tablets AM and 1 tablet PM Day 2: 6 mg: Take 1 tablet AM and 0 tablets PM Days 3–7: 6 mg: Take 1 tablet AM and 1 tablet PM
12 mg	2	6 mg	n/a	n/a	6 mg: Take 1 tablet AM and 1 tablet PM
18 mg	2	9 mg	n/a	n/a	9 mg: Take 1 tablet AM and 1 tablet PM
24 mg	2	12 mg	n/a	n/a	12 mg: Take 1 tablet AM and 1 tablet PM
30 mg	2	6 mg	2	9 mg	6 mg: Take 1 tablet AM and 1 tablet PM 9 mg: Take 1 tablet AM and 1 tablet PM
36 mg	4	9 mg	n/a	n/a	9 mg: Take 2 tablets AM and 2 tablets PM
42 mg	2	9 mg	2	12 mg	9 mg: Take 1 tablet AM and 1 tablet PM 12 mg: Take 1 tablet AM and 1 tablet PM
48 mg	4	12 mg	n/a	n/a	12 mg: Take 2 tablets AM and 2 tablets PM

This document is confidential.

Table 5: Part II and Part III Re-Titration or Blinded Maintenance Period Administration Instructions

Last Dose Dispensed in Part A Maintenance	Bottle A Dispensed	Bottle B Dispensed	Dispensation Instructions
6 mg	Yes	n/a	Bottle A: Take 1 tablet AM and 0 tablet PM
12 mg	Yes	n/a	Bottle A: Take 1 tablet AM and 1 tablet PM
18 mg	Yes	n/a	Bottle A: Take 1 tablet AM and 1 tablet PM
24 mg	Yes	n/a	Bottle A: Take 1 tablet AM and 1 tablet PM
30 mg	Yes	n/a	Bottle A: Take 1 tablet AM and 1 tablet PM
36 mg	Yes	n/a	Bottle A: Take 1 tablet AM and 1 tablet PM
42 mg	Yes	Yes	Bottle A: Take 1 tablet AM and 1 tablet PM Bottle B: Take 1 tablet AM and 1 tablet PM
48 mg	Yes	Yes	Bottle A: Take 1 tablet AM and 1 tablet PM Bottle B: Take 1 tablet AM and 1 tablet PM

If a patient does not return a pill bottle, it will be assumed that the patient took no study drug from that bottle for the purposes of calculating compliance. If the first or last dose date is missing, the date of the previous visit and the day before current visit will be used as the first and last dose. The total assigned daily dose is not collected for the blinded period and the last assigned dose before Week 28 will be used. Compliance will also be summarized by categories <80%, 80% - < 105%, and >105%. Compliance will be summarized for Parts I and III combined based the Safety Analysis Set, Part II, based on the RWSAF Population.

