- ^v Study drug will be dispensed in the clinic; patients will receive doses for 2 weeks (current dose level and next dose level) to cover the telephone contacts. The site will determine titration (ie, starting the next dose) for the patient by telephone.
- ^w Patients will receive enough doses to cover treatment until the following in-clinic visit.^z
- ^x The site needs to discuss the drug status during the telephone contacts to ensure the patient has adequate tablets, inform the patient if they should titrate (only during the titration period), and remind them to bring completed bottles to the next in-clinic visit.
- ^y Parents/Patients will be instructed during the course of the study to notify the investigator if any new medication is prescribed/administered, including over-the-counter medications. Any prescribed medication should be reviewed with the investigator.
- ^z Genotype data will be obtained from the relevant parent study.

ADHD=Attention Deficit Hyperactivity Disorder; β -HCG=beta human chorionic gonadotropin; BP=blood pressure; CDI-2=Children's Depression Inventory, Second Edition, Parent and Self-Report Profiles; CSR=clinical study report; C-SSRS=Columbia-Suicide Severity Rating Scale; CY-BOCS=Children's Yale-Brown Obsessive-Compulsive Scale; CYP2D6=cytochrome P450 2D6; ECG=electrocardiogram; ET=early termination visit; C&A-GTS-QOL=Child and Adolescent Gilles de la Tourette Syndrome – Quality of Life; IMP=Investigational Medicinal Product; MINI Kid=Mini International Neuropsychiatric Interview For Children and Adolescents (version 6.0); TS-CGI=Tourette Syndrome-Clinical Global Impression; OCD=obsessive-compulsive disorder; TS-PGII=Tourette Syndrome-Patient Global Impression of Impact; TS-PGIS=Tourette Syndrome-Patient Global Impression of Severity; U=unscheduled visit; UA=urinalysis; VAS=visual analog scale; YGTSS=Yale Global Tic Severity Scale.

This document is confidential.

Statistical Analysis Plan for Interventional Studies

Sponsor: Teva Branded Pharmaceutical Products R&D, Inc./Nuvelution TS Pharma, INC.

Protocol No.: TV50717-CNS-30047

Table 3: Study Procedures and Assessments (continued)

	Part II			Part III									U
	Randomized drug withdrawal			Maintenance (resumed) or titration post-drug withdrawal			Maintenance			Follow-up			
Study week ^a	28 ^b (Day 196)	29 (Day 203)	30 (Day 210)	31 (Day 217)	32 (Day 224)	33 (Day 231)	34 (Day 238)	41 (Day 287)	47 (Day 329)	54/ET ^c (Day 378)	55 (Day 385)	56 ^d (Day 392)	

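### The expected-tablet count for compliance rests on a Table 4 row that contradicts itself (7 against 12 tablets a week), and Section 9.2 leaves unstarted next-dose bottles, exactly 105% and the counting unit undefined

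*SAP*

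**What the plan says.** SAP Section 9.2 computes compliance in three steps. It totals the pills taken over all dispensed bottles. It then sets the denominator: "The number of pills expected = sum (the number of pills should be taken per schedule for all bottles dispensed", referring to Tables 4 and 5. Finally it takes the ratio: "Treatment compliance (%) = 100*(total number of doses taken / number of doses expected to be used".

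Table 4 has nine daily-dose rows, each with a tablets-per-day column and written instructions. The 6/12 mg row gives 1 tablet of 6 mg per day. Its instructions are "Day 1: 6 mg: Take 0 tablets AM and 1 tablet PM", then "Day 2: 6 mg: Take 1 tablet AM and 0 tablets PM Days 3–7: 6 mg: Take 1 tablet AM and 1 tablet PM".

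On supply during Part I titration, footnote v to Table 3 (Section 3.8) states that "patients will receive doses for 2 weeks (current dose level and next dose level) to cover the telephone contacts". It adds: "The site will determine titration (ie, starting the next dose) for the patient by telephone".

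Section 9.2 also says that the assigned total daily dose and the first and last dose times are collected in the open-label portion. For the blinded period the assigned dose is not collected, and the last one before Week 28 is used. The bands are "Compliance will also be summarized by categories <80%, 80% - < 105%, and >105" per cent. Compliance is summarized for Parts I and III combined (Safety Analysis Set) and for Part II (RWSAF).

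**The concern.** Table 4 supplies the denominator, so a row whose two halves disagree gives two compliance values for the same patient, and the programmer has to choose between them.

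The bottle rule raises a second question. The current and next dose levels can be handed out together, and the decision to start the next one comes later by telephone. A sum over everything dispensed, with no statement about a bottle that was never to be started, could enlarge the denominator for a patient who did exactly as told.

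Two smaller defects sit in the same section. A value of exactly 105% has no band, and the first two steps count pills while the ratio speaks of doses.

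At stake is the accuracy of a descriptive table in a study whose primary objective is safety and tolerability. The patients most exposed are those who leave early. They are in the Safety Analysis Set and have little later dosing to dilute an error made during titration.

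**Working it through.** **1. Table 4, row by row (tablets per week).** Column figure × 7 against the sum of the instructions over seven days:

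- 6 mg: 7 and 7.
- 12, 18 and 24 mg: 14 and 14.
- 30, 36, 42 and 48 mg: 28 and 28.
- 6/12 mg: column 1 × 7 = 7; instructions 1 + 1 + 5 × 2 = 12.

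Eight rows agree and one does not.

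**2. Effect in that week.**

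- 12 tablets taken: 12/12 = 100% by the instructions, 12/7 = 171.4% by the column.
- 7 tablets taken: 7/12 = 58.3% by the instructions, 7/7 = 100% by the column.

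Each pair falls in two different bands.

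**3. Carry-over.** Assumptions: the row covers the first treatment week, the patient takes 2 tablets a day afterwards, adherence is perfect, and the column is used for the denominator. After w weeks, compliance = (12 + 14(w − 1)) / (7 + 14(w − 1)).

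- w = 2: 26/21 = 123.8%.
- w = 7: 96/91 = 105.5%.
- w = 8: 110/105 = 104.8%.
- w = 52 (28 weeks of Part I plus Weeks 31 to 54): 726/721 = 100.7%.

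The patient is wrongly placed above 105% only with about seven weeks of data or fewer.

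**4. Unstarted next-dose bottles, if they are counted.** Assumption: the patient is held at the current level for both weeks of one dispensing interval. The split of supply between levels is not spelled out, so two splits are shown.

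- Tablets per day double (6 to 12 mg, 1 to 2; 24 to 30 mg, 2 to 4). One week expected from each level: 14/21 or 28/42 = 66.7%. Two weeks at the current level plus one at the next: 14/28 or 28/56 = 50.0%.
- Tablets per day equal (for example 12 to 18 mg). One week from each level: 28/28 = 100%. Two weeks plus one: 28/42 = 66.7%.

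Over the whole exposure, suppose n unstarted sets each add one week of next-level tablets to an otherwise perfect record of w weeks. Compliance is then w / (w + n × r), where r is the ratio of next to current tablets per day.

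- w = 52, r = 2: 52/54 = 96.3% (n = 1) to 52/60 = 86.7% (n = 4).
- w = 52, r = 1: 52/53 = 98.1% (n = 1) to 52/56 = 92.9% (n = 4).
- n = 1, below 80%: w/(w + 2) < 0.8 gives w < 8 when r = 2; w/(w + 1) < 0.8 gives w < 4 when r = 1.

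Even if the bottles count, a fully adherent completer stays above 80%. The effect is confined to early leavers, and mostly to steps where tablets per day double.

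**5. Bands and unit.** The middle band stops below 105% and the top band starts above it. An exact 105% needs an expected count that is a multiple of 20 (for example 21 taken of 20), so it is rare but possible. Pills and doses are not interchangeable as counts: at 36 and 48 mg each intake is 2 tablets.

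**The case against.** The strongest defence of the row is that the denominator follows the schedule, the schedule is the written instructions, and the 1 sits under a kit-supply heading. On that reading the adherent patient scores 12/12 and nothing is wrong. This is plausible but not stated. In the other eight rows the column reproduces the instructions, so a programmer has good reason to treat it as the daily count. How many patients used the row is unknown, and anyone who moves to 4 tablets a day drops below 105% sooner than shown.

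On the bottles, a reader might infer that the rule does count those a patient was told not to start, so that patients held for tolerability appear under-compliant. The SAP does not support that. It counts pills that should be taken, which allows an expected count of 0. It also collects the assigned dose and dose dates, and it uses the last assigned dose for the blinded period, which suggests that assigned dose is meant to drive the count. The 66.7% figures apply to one interval, for which no summary is planned, and they rest on an assumed split. At 24 to 30 mg, 28 current-level tablets could not come from one week's supply of each level, because 30 mg uses other strengths. At 6 to 12 mg both levels use 6 mg tablets, so the second bottle might supply the held dose. These objections stand. What remains is that no sentence settles the matter, and the assigned-dose sentence covers only the blinded period.

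Finally, compliance enters no analysis-set definition and no efficacy model. That stands too, and it limits the severity.

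**Conclusion.** The contradiction in the 6/12 mg row is plain, 7 tablets against 12, and must be reconciled because the row feeds a reported figure. If the column is used, an adherent patient reads 171% for that week, stays above 105% through Week 7 and reads about 100.7% at 52 weeks. This assumes 2 tablets a day after the first week. Mainly early withdrawals are misclassified.

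Unstarted next-dose bottles are an ambiguity that needs one sentence, not an error shown in the plan. The 105% gap and the change from pills to doses are certain but small.

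It would go too far to call the expected count wrong throughout dose escalation. Eight of nine rows are consistent, and where tablets per day are equal between levels, pooling pills over strengths can hide the bottle question altogether. Severity is minor. The 52-week figures assume full exposure in Parts I and III, and up to four unstarted bottle sets is an assumption.

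**What to change.** - Reconcile the tablets-per-day entry and the instructions in the 6/12 mg row of Table 4. Which of the two is right is for the sponsor to decide.
- For the open-label weeks, define expected pills as the sum, over days from first to last dose, of the tablets per day for the assigned daily dose on the CRF. State that a bottle the patient was not told to start has an expected count of 0.
- For the blinded weeks, including those in Part III, keep the existing rule (last assigned dose before Week 28, with Table 5), since the assigned dose is not collected there.
- Make the middle category 80% to ≤105%.
- Use pills in all three steps.

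The cost is SAP wording and programming only. The open-label assigned dose and dose dates are already collected. The change should be made before database lock.
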